7.4.2.2. MPN-SAF

The MPN-SAF weekly total score is defined as the sum of 10 individual symptom scores (fatigue, nights sweats, itchiness, bone pain, fever, unintentional weight loss last 6 months, early satiety, abdominal discomfort, inactivity, problems with concentration, each with a 0 to 10 point scale) collected at the same visit; the score will be missing if there are any missing individual scores.

The number of participants with reductions in MPN-SAF TSS from baseline to every 4 weeks will be summarized categorically, and a Cochran-Mantel-Haenszel test will be applied as described in Section [7.4.2.1.1](#).

7.4.3. Analysis of IWG-MRT Consensus Criteria

IWG-MRT criteria provides criteria for response to treatment in MF. Recently published response criteria developed by the IWG on MF will be used in this study ([Tefferi et al 2013](#)). Overall response assessment will be graded according to the IWG-MRT consensus criteria for treatment response in PMF, PPV-MF, and PET-MF. The criteria for response assessment according to IWG-MRT is provided in [Appendix B](#).

The IWG-MRT assessment will be performed at baseline, Week 24, and every 24 weeks thereafter. The number of participants with responses according to investigator-reported IWG-MRT consensus criteria will be summarized by treatment group. Best overall response under the IWG-MRT consensus criteria will also be summarized. Best overall response is defined as the highest overall response achieved postbaseline prior to and including the first confirmed progressive disease in the order of complete response, partial response, clinical improvement, stable disease, partial disease, and relapse. A listing of the clinical data used by Incyte to derive the IWG-MRT responses will be provided.

7.4.4. Analysis of Patient Global Impression of Change Score

The Patient Global Impression of Change questionnaire consists of question with 7 possible answers. The Patient Global Impression of Change questionnaire will be completed at each study visit. The PGIC score will be tabulated and summarized descriptively (mean, standard deviation, etc) by treatment group and by daily and daily/weekly dosing for the safety population in the initial portion at each visit.

8. SAFETY AND TOLERABILITY

The lists of tables, figures, and appendices are provided in [Appendix A](#). Sample data displays are provided in a separate document. The lists and the shells are to be used as a guideline. Modifications of the list or shells that do not otherwise affect the nature of the analysis will not warrant an amendment to the SAP.

8.1. General Considerations

Summary tables may be replaced with listings when appropriate. For instance, an AE frequency table may be replaced with a listing if it only contains a few unique PTs reported on relatively few participants.

8.2. Adverse Events

8.2.1. Adverse Event Definitions

A TEAE is any AE either reported for the first time or worsening of a pre-existing event after first dose of study drug. Analysis of AEs (as discussed below) will be limited to TEAEs, but data listings will include all AEs regardless of their timing in relation to study drug administration.

Adverse events will be tabulated by MedDRA PT and SOC. Severity of AEs will be graded using the NCI CTCAE. The CTCAE version 4.03 is used for this study. The CTCAE reporting guidelines and grading details are available on the Cancer Therapy Evaluation Program website.

The subset of AEs considered by the investigator to be related to study drug will be considered to be treatment-related AEs. If the investigator does not specify the relationship of the AE to study drug, the AE will be considered to be treatment-related. The incidence of AEs and treatment-related AEs will be tabulated. In addition, SAEs will be tabulated.

Any missing onset date, causality, or severity must be queried for resolution. Unresolved missing causality and severity will be handled according to the following rules:

- An unresolved missing causality will be considered treatment-related.
- An unresolved missing severity will be identified as an unknown severity.

For purposes of analysis, all AEs will be considered TEAEs unless the AE can unequivocally be defined as not treatment emergent.

8.2.2. Dose-Limiting Toxicities

A DLT or dose limiting toxicity will be defined as the occurrence of a toxicity, with the exception of events clearly associated with the underlying disease, disease progression, a concomitant medication, or comorbidity; the list of toxicities that will be designated as DLTs are provided in Table 3 of the Protocol.

The number of participants with DLTs and the type of DLT will be listed by treatment group.

8.2.3. Maximum Tolerated Dose

The MTD of INCB050465 is the highest treatment group tested that is considered tolerated on the basis of fewer than 2 DLTs in a cohort of 6 participants.

8.2.4. Adverse Events of Special Interest

The principle toxicity of inhibiting both PI3K δ and JAK pathways is expected to be reversible effects on immune function. Combined inhibition may adversely affect both B-cell and T-cell immune function with resultant increased risk of a variety of infections or other immune-related events. Infections and inflammation reactions will be monitored and comprise AEs of special interest as indicated in [Table 5](#).

Liver chemistry tests as assessed by ALT, AST, total bilirubin, alkaline phosphatase tests are also considered as events of special interest and will be summarized for the safety population by dose group for initial portion and crossover portion separately. Participants with elevations in liver chemistry tests will be summarized, and a listing for participants with ALT $\geq 5 \times$ ULN or AST $\geq 5 \times$ ULN will be provided.

Specific AEs, or groups of AEs, will be followed as part of standard safety monitoring activities. The number and proportion of participants experiencing the events listed in [Table 5](#) (regardless of seriousness) will be summarized by treatment group. The AESIs will be summarized for the safety population by dose group for the initial portion and crossover portion separately.

Table 5: Adverse Events of Special Interest

Category of AEs	Specific AEs in Category
Liver Chemistry Tests	ALT/AST elevations equal to or above $5 \times$ ULN
Inflammation/reactions	Colitis, diarrhea \geq Grade 2, rash \geq Grade 2, pneumonitis, exfoliative dermatitis, intestinal perforation
Infections	CMV infection, herpes simplex virus infection, varicella zoster virus infection, Pneumocystis jirovecii infection

8.2.5. Adverse Event Summaries

An overall summary of AEs by treatment group will include:

- Number (%) of participants reporting any TEAEs
- Number (%) of participants reporting any DLTs
- Number (%) of participants reporting any SAEs
- Number (%) of participants reporting any Grade 3 or 4 TEAEs
- Number (%) of participants reporting any TEAEs related to INCB050465
- Number (%) of participants reporting any TEAEs related to ruxolitinib
- Number (%) of participants who temporarily interrupted INCB050465 because of TEAEs

- Number (%) of participants who temporarily interrupted ruxolitinib because of TEAEs
- Number (%) of participants who permanently discontinued INCB050465 because of TEAEs
- Number (%) of participants who permanently discontinued ruxolitinib because of TEAEs
- Number (%) of participants with INCB050465 dose reductions because of TEAEs
- Number (%) of participants with ruxolitinib dose reductions because of TEAEs
- Number (%) of participants who had a fatal TEAE
- Number (%) of participants who withdrew from study because of an TEAE
- Number (%) of participants reporting any treatment-emergent AESIs

The following summaries will be produced by MedDRA term (if 10 or fewer participants appear in a table, a listing may be appropriate):

- Summary of TEAEs by SOC and PT
- Summary of TEAEs by PT in decreasing order of frequency
- Summary of TEAEs by SOC, PT, and maximum severity
- Summary of Grade 3 or 4 TEAEs by SOC and PT
- Summary of INCB050465 treatment-related AEs by SOC and PT
- Summary of Grade 3 or 4 INCB050465 treatment-related AEs by SOC and PT
- Summary of INCB050465 treatment-related AEs by SOC, PT, and maximum severity
- Summary of ruxolitinib treatment-related AEs by SOC and PT
- Summary of Grade 3 or 4 ruxolitinib treatment-related AEs by SOC and PT
- Summary of ruxolitinib treatment-related AEs by SOC, PT, and maximum severity
- Summary of TEAEs leading to death by SOC and PT
- Summary of treatment-emergent SAEs by SOC and PT
- Summary of treatment-emergent SAEs by PT in descending order of frequency
- Summary of INCB050465 treatment-related SAEs by SOC and PT
- Summary of ruxolitinib treatment-related SAEs by SOC and PT
- Summary of TEAEs leading to INCB050465 dose reduction by SOC and PT
- Summary of TEAEs leading to ruxolitinib dose reduction by SOC and PT
- Summary of TEAEs leading to INCB050465 dose interruption by SOC and PT
- Summary of TEAEs leading to ruxolitinib dose interruption by SOC and PT

- Summary of TEAEs leading to discontinuation of INCB050465 by SOC and PT
- Summary of TEAEs leading to discontinuation of ruxolitinib by SOC and PT
- Summary of TEAEs by SOC and PT: life-table method
- Summary of treatment-emergent AESIs

8.3. Clinical Laboratory Tests

8.3.1. Laboratory Value Definitions

Laboratory values and change from baseline values will be summarized descriptively by visit. Baseline will be determined according to Section 4.1.4. If there are multiple values that meet the criteria for baseline, additional rules may be provided after consultation with the medical monitor to delineate which value will be defined as baseline.

Laboratory test values outside the normal range will be assessed for severity based on CTCAE grade where clinical intervention is required for CTCAE grading. The incidence of abnormal laboratory values and shift tables relative to baseline will be tabulated.

8.3.2. Laboratory Value Summaries

All test results and associated normal ranges from central laboratories will be reported in SI units. All tests with numeric values will have a unique unit per test. Any laboratory test results and associated normal ranges from local laboratories will be converted to SI units. For the limited number of cases where the associated normal ranges from a local laboratory cannot be obtained despite due diligence, if query is unsuccessful at resolving the issues and analysis is mandatory, then the clinical scientist and medical monitor can provide a suitable normal range to be used in determining CTC grading and flags for above and below normal.

When there are multiple laboratory nonmissing values for a participant's particular test within a visit window, the convention described in [Table 6](#) will be used to determine the record used for by-visit tabulations and summaries.

Table 6: Identification of Records for Postbaseline By-Visit Summaries

Priority	Laboratory Visit	Central or Local Laboratory	Proximity to Visit Window	Tiebreaker
1	Scheduled	Central	In-window	Use smallest laboratory sequence number
2	Scheduled	Local	In-window	
3	Unscheduled	Central	In-window	
4	Unscheduled	Local	In-window	
5	Scheduled	Central	Out-of-window	
6	Scheduled	Local	Out-of-window	

Shift tables based on worst postbaseline value recorded will use all postbaseline values occurring within 30 days of stopping study treatment.

Numeric laboratory values will be summarized descriptively in SI units, and non-numeric test values will be tabulated when necessary. In addition, line graphs and box-and-whisker plots will be provided for Hgb, platelet counts, WBC, and neutrophils.

For test results that will be summarized with available normal ranges, the number and percentage of participants with the laboratory values being low (but never high), normal, high (but never low), and both low and high will be calculated for each test. This shift summary will be produced for each test for the safety population. The denominator for the percentage calculation will use the number of participants in the baseline category (ie, low, high, normal, missing) as the denominator for the percentage in each of the categories during the treatment period.

Shift tables will be presented showing change in CTCAE grade from baseline to worst grade postbaseline. Separate summaries for abnormally high and abnormally low laboratory values will be provided when the laboratory parameter has both high and low grading criteria. The denominator for the percentage calculation will be the number of participants in the baseline category.

In cases where differentials of hematology parameters are obtained without corresponding absolute count data, efforts will be made to investigate if the conversion to an absolute value will lead to additional abnormalities. This will be discussed with the clinical team regarding appropriate documentation and action.

Participants with the following elevations in liver chemistry tests will be summarized by treatment group for the safety population:

- ALT > 5 × ULN
- AST > 5 × ULN
- ALT or AST > 5 × ULN
- TBL > 2 × ULN
- ALT or AST > 5 × ULN and TBL > 2 × ULN and ALP < 2 × ULN

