**Table 5: Guidelines for Interruption and Restarting of INCB050465**

ADVERSE EVENT	ACTION TAKEN
Chemistry	

AST and/or ALT are <math>> 5.0 \times</math> ULN.

 
Note: In subjects with bone metastasis-related elevations at baseline, contact sponsor to discuss clinical management and possible dose reductions.
	
Step 1: Interrupt study drug up to 2 weeks (14 days) until the toxicity has resolved to <math>\leq</math> Grade 1 except by approval of the medical monitor.
 
Step 2: Restart study drug at same dose. If assessed as related to study drug, restart study drug at next lower dose (or at 25% reduction, rounded down to the nearest pill strength); monitor as clinically indicated.

Hematology	

ANC <math>\leq 1.0 \times 10^9/L</math> unless because of underlying disease. Applies only if this represents a worsening grade from baseline.

Platelet count <math>\geq 50 \times 10^9/L</math> and <math>< 75 \times 10^9/L</math> unless because of underlying disease. Applies only if this represents a worsening grade from baseline.

	
Step 1: Interrupt study drug up to 2 weeks (14 days) until the toxicity has resolved to <math>\leq</math> Grade 1 or pretherapy baseline.
 
Step 2: Restart study drug at same dose and monitor as clinically indicated.

Grade 4 ANC (<math>< 0.5 \times 10^9/L</math>) regardless of baseline grade.

<math>\geq</math> Grade 3 ANC with an oral temperature of at least <math>38.5^\circ C</math> OR with <math>\geq</math> Grade 3 infection regardless of baseline grade.

Platelet count is <math>< 50 \times 10^9/L</math>, regardless of baseline grade.

	
Step 1: Interrupt study drug up to 2 weeks (14 days) until the toxicity has resolved to <math>\leq</math> Grade 1 or pretherapy baseline.
 
Step 2: Restart study drug at same dose. If assessed as related to study drug, restart study drug at next lower dose; monitor as clinically indicated.

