**Table 9: Schedule of Laboratory Assessments – Part 1, Part 2, Part 3, and Part 4**

	Screening	Baseline	Day 1	Weeks 1, 3 (Day 8, 22) Part 1 ONLY	End of Weeks 2, 6, 10, 14, 18, 22, then Q4W	End of Weeks 4, 8, 12, 16, 20, 24, then Q12W	EOT or Early Termination Visit	Follow-Up 30-37 Days After Last Dose of INCB050465	Notes		
Window				The window for laboratory visits is ± 3 days							
Local Laboratory Assessments											
Serum chemistries	X	X*	X*	X		X	X	X	*Should be taken as close as possible to Day 1 but may be drawn up to 3 days before first dose. Only 1 sample for baseline/Day 1 is required.		
Hematology	X	X*	X*	X	X	X	X	X	*Should be taken as close as possible to Day 1 but may be drawn up to 3 days before first dose. Only 1 sample for baseline/Day 1 is required.		
Coagulation panel	X					X*	X	X	*Required Weeks 12 and 24 and Q12W.		
Urine pregnancy test		X				X*	X*		All female subjects of childbearing potential. *Pregnancy tests should be repeated if required by local regulations.		
Bone marrow biopsy, aspirate, and analysis	X*					X**			*Predose biopsy/aspirate is not required if biopsy has occurred in previous 2 months as long as biopsy/aspirate and data are available for review by investigator and/or sponsor. **Week 24 and Q24W. Samples of biopsy and unstained slides will be sent to a central vendor.		
Central Laboratory Samples*									*The central laboratory is the sponsor or sponsor's designee.		
Lipid panel (requires overnight fast)	X					X*	X		*Required Weeks 12 and 24 and Q12W.		
Serology - hepatitis and HIV	X								HBV, HCV, HIV		
Serology - CMV	X					X*			* CMV measured at Weeks 4, 8, 12, then Q12 weeks.		
Urinalysis	X					X*		X	*Required Weeks 12 and 24 and Q12W.		
Serum pregnancy	X							X	All female subjects of childbearing potential.		
FSH	X								To document hormonal menopause.		
PK samples			X		X*	X*			*PK sampling will occur on Day 1, Week 2, and Week 4 only. See Table 8 .		

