#### 9.4.2.5. Adverse Events of Special Interest

The principle toxicity of inhibiting both PI3K $\delta$  and JAK pathways is expected to be reversible effects on immune function. Combined inhibition may adversely affect both B-cell and T-cell immune function with resultant increased risk of a variety of infections or other immune-related events. Specific AEs, or groups of AEs, will be followed as part of standard safety monitoring activities. These events (regardless of seriousness) will be reported per the SAE reporting timelines (see [Section 8.3.2](#)).

- ALT  $\geq$  5  $\times$  ULN
- AST  $\geq$  5  $\times$  ULN
- Colitis
- Diarrhea  $\geq$  Grade 2

- Rash  $\geq$  Grade 2
- Intestinal perforation
- Pneumonitis
- *Pneumocystis jirovecii* infection
- CMV infection
- Herpes simplex virus infection
- Varicella zoster virus infection
- Exfoliative dermatitis

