3.3 Laboratory			
3.3.1.1	Summary of Laboratory Values – Hematology	Safety Initial Portion	X
3.3.1.2	Summary of Laboratory Values – Hematology	Safety Crossover Portion	X
3.3.2.1	Shift Summary of Hematology Laboratory Values in CTC Grade – To the Worst Abnormal Value	Safety Initial Portion	X
3.3.2.2	Shift Summary of Hematology Laboratory Values in CTC Grade – To the Worst Abnormal Value	Safety Crossover Portion	X
3.3.3.1	Summary of Laboratory Values – Chemistry	Safety Initial Portion	X
3.3.3.2	Summary of Laboratory Values – Chemistry	Safety Crossover Portion	X
3.3.4.1	Shift Summary of Chemistry Laboratory Values in CTC Grade – To the Worst Abnormal Value	Safety Initial Portion	X
3.3.4.2	Shift Summary of Chemistry Laboratory Values in CTC Grade – To the Worst Abnormal Value	Safety Crossover Portion	X
3.3.5.1	Summary of Laboratory Values – Coagulation	Safety Initial Portion	X
3.3.5.2	Summary of Laboratory Values – Coagulation	Safety Crossover Portion	X
3.3.6.1	Shift Summary of Coagulation Values in CTC Grade – To the Worst Abnormal Value	Safety Initial Portion	X
3.3.6.2	Shift Summary of Coagulation Values in CTC Grade – To the Worst Abnormal Value	Safety Crossover Portion	X
3.3.7.1	Summary of Participants With Elevations in Liver Chemistry Tests	Safety Initial Portion	X
3.3.7.2	Summary of Participants With Elevations in Liver Chemistry Tests	Safety Crossover Portion	X

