2.8 Laboratory Data	
2.8.1	Clinical Laboratory Values – Hematology
2.8.2	Clinical Laboratory Values – Chemistry
2.8.3	Clinical Laboratory Values – Coagulation
2.8.4	Clinical Laboratory Values – Serology
2.8.5	Abnormal Clinical Laboratory Values
2.8.6	Participants With AST $\geq 5 \times$ ULN or ALT $\geq 5 \times$ ULN

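### The liver summary joins transaminases with bilirubin only above 5 × ULN, so a lower rise with bilirubin above 2 × ULN is never counted as a combined case

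*SAP*

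**What the plan says.** **Rows.** SAP 8.3.2 asks for five counts by treatment group: ALT above 5 × ULN, AST above 5 × ULN, either above 5 × ULN, total bilirubin (TBL) above 2 × ULN, and the joint row "ALT or AST > 5 × ULN and TBL > 2 × ULN and ALP < 2 × ULN".

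**Tables and listings.** Appendix A gives these counts one table title, "Summary of Participants With Elevations in Liver Chemistry Tests", produced once for the initial portion (3.3.7.1) and once for the crossover portion (3.3.7.2). Both are marked as standard tables. The dedicated liver listing (2.8.6) starts at 5 × ULN for AST or ALT. The full chemistry data go to Listing 2.8.2, "Clinical Laboratory Values – Chemistry", and abnormal values to Listing 2.8.5.

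**Special interest.** SAP 8.2.4 states: "Liver chemistry tests as assessed by ALT, AST, total bilirubin, alkaline phosphatase tests are also considered as events of special interest". SAP Table 5 then sets a limit only for ALT/AST, at 5 × ULN or more.

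**Window.** SAP 8.3.2 says that shift tables of worst values "will use all postbaseline values occurring within 30 days of stopping study treatment". The liver rows carry no window or pairing rule of their own in that section.

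**Where 5 × ULN comes from.** For AST and/or ALT above 5.0 × ULN, Protocol Table 5 begins: "Interrupt study drug up to 2 weeks (14 days) until the toxicity has resolved to" Grade 1 or lower. Protocol 9.4.2.5 lists ALT or AST at 5 × ULN or more as special-interest events and adds: "These events (regardless of seriousness) will be reported per the SAE reporting timelines".

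**The concern.** Protocol 1.8.4 names hepatotoxicity as a risk of the drug class, and safety of the combination is a secondary objective. A transaminase rise together with a bilirubin rise tells a reviewer more than either alone, and the plan accepts this by having a joint row. That row uses the highest transaminase cut-off in the plan. A participant with ALT 4.8 × ULN and TBL 4 × ULN is outside it.

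The bilirubin row does include this participant, but it cannot separate the case from an isolated or pre-existing bilirubin rise. Exclusion criterion 5a acts on direct bilirubin, so someone with raised total but acceptable direct bilirubin can enter the trial. In a small study that ended early, the joint row may well read zero, and a reader could take that zero as broader reassurance than it gives.

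**Working it through.** **1. Which row catches which case.** The five rows of SAP 8.3.2, applied to constructed values (× ULN):

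| Larger of ALT and AST | TBL | ALP | Rows entered | In joint row? |
|---|---|---|---|---|
| 3.5 | 2.5 | 1 | TBL >2 | no |
| 4.9 | 3 | 1 | TBL >2 | no |
| 5.0 | 2.5 | 1 | TBL >2 (also special interest at ≥5) | no |
| 5.1 | 2.5 | 1 | transaminase rows, TBL >2, joint | yes |
| 5.1 | 2.5 | 2.0 | transaminase rows, TBL >2 | no (ALP not <2) |

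Every case at or below 5 × ULN with TBL above 2 × ULN misses the joint row.

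**2. Does another specified summary supply the joint count?** The CTCAE and low/normal/high shift tables (SAP 8.3.2; Protocol 9.4.2.2) include the case but handle one test at a time. The special-interest category (SAP Table 5) has no bilirubin condition. Listings 2.8.2 and 2.8.5 show the values without counting. Appendix A has no other liver summary table. So the answer is no.

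**3. What a lower row adds, and why one timing rule is needed.** Six constructed profiles (× ULN; ALP 1 unless stated):

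- A: ALT 4.8 and TBL 4 on one date.
- B: ALT 5.2 and TBL 4 on one date.
- C: ALT 6 on Day 57, TBL 3 on Day 85.
- D: ALT 4 on Day 57, TBL 3 on Day 85.
- E: TBL 2.5, ALT 1.
- F: ALT 4, TBL 4, ALP 3.

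| Rule | Joint >5 | Joint >3 |
|---|---|---|
| All conditions on the same date | 1 (B) | 2 (A, B) |
| Peak ALT/AST, peak TBL, ALP on the transaminase-peak date | 2 (B, C) | 4 (A to D) |

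The TBL row counts all 6. Either rule, used for both rows, nests: anyone in the >5 row is also in the >3 row. Mixing the rules does not, because C would count at >5 (peak) but not at >3 (same date).

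**4. A weakness of the peak rule.** Take Day 57 with ALT 4.5, TBL 3, ALP 2.5, and Day 85 with ALT 4, TBL 3, ALP 1. On Day 85 all conditions of a >3 row hold together, so the same-date rule counts this participant. The peak rule reads ALP on Day 57 (2.5, not below 2) and misses the case.

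**5. Illustration of a zero count.** Assume a proportion *p* has a combined case above 3 × ULN and a fraction *f* of those lies at 3 to 5 × ULN. Neither figure is in the documents. The chance of a zero is (1 − *p*)^n for a >3 row and (1 − *p*(1 − *f*))^n for the >5 row. For example, with n = 30, *p* = 0.02 and *f* = 0.5: 0.98^30 = 0.545 and 0.99^30 = 0.740.

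| n | >3 row, *p* = 2% | >5 row, *f* = 25% / 50% / 75% |
|---|---|---|
| 30 (enrolled in Parts 1 and 2: 10 + 20) | 55% | 64% / 74% / 86% |
| 60 | 30% | 40% / 55% / 74% |
| 90 (Protocol 4.3.1: 10 + 20 + 5 + 55) | 16% | 26% / 40% / 64% |

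For *p* from 1% to 5%, the n = 30 figures run from 74% to 21% (>3 row) against 93% to 32% (>5 row, across all *f*). At n = 90 they run from 40% to 1% against 80% to 3%.

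**The case against.** The best defence is that nothing here is wrong. The joint row uses the plan's own on-treatment limit, no data are lost, and no management rule or efficacy result changes. No passage sets a limit of 3 × ULN; 2.5 × ULN is an entry and crossover limit, not a safety-signal criterion. All of this stands, and it fixes the weight of the point. It does not remove the gap: the 5 × ULN limits concern ALT/AST alone and do not say where a combined count should start.

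Three stronger readings are tempting and not supported:

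- A reader might infer that such a case is visible only in the bilirubin row. That is true only within the five rows. The case also enters the single-test shift tables and Listings 2.8.2 and 2.8.5, and the adverse event tables if the investigator reports it (Protocol 8.2). The shift tables also show, test by test, whether bilirubin was already raised at baseline.
- A reader might infer that the sponsor has no timing rule for the joint row. SAP 8.3.2 states none, but Appendix A says standard tables follow a Standard Safety Tables convention, and the shells are in a separate document. Neither was available, so a rule or further rows may exist there.
- A reader might take the zero-count percentages as this trial's chances. They rest on assumed rates and a pooled n, whereas the table is by treatment group and split by portion, and the study ended early. They show only that a lower cut-off catches more.

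**Conclusion.** The point holds as a cheap, minor improvement to safety reporting. No summary table specified in the SAP counts a transaminase rise at or below 5 × ULN with TBL above 2 × ULN as a combined case. In the constructed profiles, a >3 row raises the joint count from 1 to 2 of 6 under a same-date rule. A cut-off of 2.5 also gives 2 (A and B; C to F fail on date, ALT or ALP).

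The size in the real trial cannot be derived, since the documents give no event rate. The conclusion rests on the SAP text and Appendix A as published; an unseen shell or standard convention could already close the gap. The claim that a lower joint cut-off is useful rests on the stated class risk and safety objective, and the value 3 is a choice.

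**What to change.** Keep the five rows and add two to Tables 3.3.7.1 and 3.3.7.2:

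- (a) ALT or AST above 3 × ULN.
- (b) ALT or AST above 3 × ULN with TBL above 2 × ULN and ALP below 2 × ULN.

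If the sponsor prefers a cut-off already in the documents, use 2.5 × ULN (Protocol 3.3 and 5.2.3). Count postbaseline values up to 30 days after stopping study treatment, the window already set for the shift tables. Require all conditions on the same date, for both joint rows, so that they nest. If the Standard Safety Tables convention already sets a timing rule, apply that rule to both rows. Do not read ALP on the transaminase-peak date. Flag participants whose baseline TBL, ALT or AST already exceeded the cut-off.

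**Cost.** Two rows, one sentence on timing and one flag. ALT, AST, ALP and total bilirubin belong to one chemistry panel (Protocol Table 10), scheduled at "End of Weeks 4, 8, 12, 16, 20, 24, then Q12W", end of treatment and follow-up, plus Days 8 and 22 in Part 1. SAP 8 lets the list or shells change without an amendment when the nature of the analysis is unaffected.

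**Downside.** A few non-specific cases will need medical review. A same-date rule will not count a bilirubin rise that follows the transaminase rise at a later visit, as in profiles C and D.
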